### **8.1.1                    Datasets for Analysis**

#### **8.1.1.1                Modified Intent-to-Treat Analysis Set**

The modified intent-to-treat (MITT) analysis set includes all randomized subjects who have taken at least one dose of study drug in the double-blind induction period. For the MITT analysis set, subjects are assigned to a treatment group based on the randomization schedule, regardless of the treatment actually received. The MITT population will also be referred as "All Randomized and Treated Subjects." The MITT analysis set will be used for all efficacy analysis for the double-blind induction period and baseline demographic and characteristics analyses.

#### **8.1.1.2                Intent-to-Treat Responder and Non-Responder Analysis Sets**

The intent-to-treat responders (ITT-R) and intent-to-treat non-responders (ITT-NR) analysis sets includes all re-randomized subjects in the double-blind extension phase who are responders and non-responders at Week 16, respectively. The clinical responder is defined as: average daily liquid/soft stool frequency at least 30% reduction from Baseline and average daily abdominal pain not worse than Baseline OR average daily abdominal pain at least 30% reduction from Baseline and average daily stool frequency not worse than Baseline. The endoscopic responder is defined as: a SES-CD at least 25% reduction from Baseline.

For the ITT-R and ITT-NR analysis sets, subjects are assigned to a treatment group based on the re-randomization schedule, regardless of the treatment actually received. The ITT-R and ITT-NR analysis sets will be used for all efficacy analysis for the double-blind extension phase.

#### **8.1.1.3 Safety Analysis Set**

The safety analysis set consists of all subjects who received at least one dose of study medication. For the safety analysis set, subjects are assigned to a treatment group based on the treatment actually received, regardless the treatment randomized.

#### **8.1.2 Subject Accountability**

The number of subjects randomized, the number of subjects who received at least one dose of study drug, the number of subjects who completed the study, and the number of subjects who prematurely discontinued will be calculated overall and for each investigational site by treatment group, as well as for all subjects combined.

#### **8.1.3 Definition of Missing Data Imputation**

Missing data will be imputed using one or more of the following methods:

**Last Observation Carried Forward (LOCF):** The LOCF analyses will use the completed evaluation from the previous visit for efficacy measures assessed to impute missing data at later visits.

**Non-Responder Imputation (NRI):** In NRI analyses, subjects who prematurely discontinue the study prior to endoscopic assessment at Week 12/16 will be considered non-responders with respect to endoscopic remission.

**Observed Cases (OC):** The OC analysis will not impute values for missing evaluations, and thus a subject who does not have an evaluation on a scheduled visit will be excluded from the OC analysis for that visit.

The stool frequency and abdominal pain scores at an assessment visit (e.g., Week 12, Week 16) will be the average of the daily values reported during the 7 usable days preceding the scheduled assessment visit.

If 7 days daily values are not available, an average will be calculated based on the number of days with available data as follows:

- An average for the most recent 6 days will be calculated if data for only 6 days are available,
- An average for the most recent 5 days will be calculated if data for only 5 days are available,
- An average for the most recent 4 days will be calculated if data for only 4 days are available.

Diary entries should not be included in the 7 days evaluated prior to the visit if: (1) the day the subject received medication for bowel preparation prior to endoscopy, (2) the day the subject underwent an endoscopy, and (3) 2 days following the endoscopy. Earlier diary entries will be used accordingly in order to provide the most recent data for 7 days prior to the respective study visit.

If the minimum number of days of diary data (i.e., 4 days for SF and AP) are not available, then the subject's score for that visit will be considered missing and NRI will be used for any endpoints (e.g., clinical remission) relating to data for this visit. Subjects who discontinue prior to Week 16 for any reason will be considered as "not-achieved" for clinical remission endpoint.

**Mixed Imputation:** Subjects who discontinue prior to Week 16 due to lack of efficacy or adverse events will be considered as "not achieved" for the clinical remission. Subjects who discontinue for other reasons will be categorized according to LOCF.

A subject will be considered a failure for the efficacy analyses at a later time points after the corticosteroid dose has been increased to greater than the dose at Baseline.

### **8.1.4 Demographics and Baseline Characteristics**

Baseline characteristics will be summarized for MITT, and ITT-R and ITT-NR analysis sets.

#### **8.1.4.1 Baseline Characteristics and Treatment Group Comparability**

Treatment groups will be compared to assess homogeneity at Baseline with respect to demographic variables such as age, gender, race, height, weight, BMI, race, ethnicity, duration of disease, vital signs (blood pressure, heart rate, and temperature), and planned efficacy assessments such as the CDAI score, average daily Abdominal Pain score, Average daily liquid/soft Stool Frequency, SES-CD and Ulcerated surface subscore, fecal calprotectin level, hs-CRP, fistula closure, IBDQ, WPAI and EQ5D.

Summary statistics for continuous variables will include the number of observations, mean, standard deviation, median, and range for each treatment group, and will be compared among treatment groups using analysis of variance (ANOVA) for normally distributed variables and Kruskal-Wallis non-parametric ANOVA for non-normally distributed variables. For other categorical or discrete variables, frequencies and percentages will be computed in each category for each treatment group, as well as for all subjects combined, and will be compared among treatment groups using chi-square test or Fisher's exact test (if 25% of the cells have expected counts less than 5).

#### **8.1.4.2 Medical Histories**

Frequencies and relative frequencies (percentages) will also be computed for each treatment group for general medical history items.

#### **8.1.4.3 Prior Therapy and Medications**

Prior therapy and medications will include all therapies and medications administered prior to the date of the first dose of study drug. Prior therapy and medication will be

summarized for all randomized subjects who received at least one dose of study drug. No statistical test will be performed.

#### **8.1.4.4 Concomitant Medications**

Concomitant drugs will be summarized for all randomized subjects who received at least one dose of study drug. Concomitant drugs will be summarized using the World Health Organization (WHO) Drug Dictionary with frequencies and percentages for each treatment group. In addition, the number and percentage of subjects taking 0, 1, 2, 3, 4, 5, and  $\geq 6$  medications, as well as the number and percentage of subjects taking at least one medication will be calculated for each treatment group. All medications administered between the date of the first dose of study drug and the date of the last dose of study drug, inclusive, (i.e., all medications starting or ongoing during the time interval) will be included. Thus, all medications with an end date prior to the first study drug dose will be excluded from the summary table. No statistical test will be performed.

A subject who reports two or more uses of the same concomitant medication will be counted only once within each generic name. A subject with concomitant medications with more than one generic name will be counted only once in the overall total.

#### **8.1.5 Subject Disposition and Study Drug Exposure**

##### **8.1.5.1 Subject Disposition**

The number and percentage of subjects who are enrolled, randomized and received at least one dose of study drug, and the number of subjects who prematurely discontinued and the reason for early termination and the number of subjects who enter the 36-week double-blind extension phase will be summarized by treatment group. Premature discontinuation of study drug will be summarized for each treatment group, as well as for all subjects combined, with frequencies and percentages overall and by reason for discontinuation for all randomized subjects who received at least one dose of study drug. Subjects may have multiple reasons for prematurely discontinuing study drug, but will be counted no more than once for the total ("Any Reason").

---

**8.1.5.2        Study Drug Exposure**

Exposure to study drug will be summarized for all subjects who have received at least one dose of study drug. The duration (days) of study drug treatment will be summarized with the mean, standard deviation, median and range for each treatment group. The duration of treatment is defined as the difference between the dates of the first and last doses of the treatment plus 1 day. Study drug compliance of the blinded study drug will be summarized for each treatment group. Compliance is defined as the number of capsules taken (i.e., the difference between the number of capsules dispensed and the number of capsules returned) divided by the number of capsules a subject is supposed to take each day times the length of time that the subject was in the Treatment Phase of the study (i.e., Final/Discontinuation Visit date during Treatment Phase – Day 1 [Baseline] Visit date +1). Subjects with missing data for the number of capsules returned will be excluded from the summary.

**8.1.6        Efficacy Analysis****8.1.6.1        Primary Efficacy Variable**

The co-primary endpoints are:

1. Proportion of subjects who achieve endoscopic remission at Week 12/16.
2. Proportion of subjects who achieve clinical remission at Week 16.

**8.1.6.1.1        Analysis of Primary Endpoint**

The comparisons between an ABT-494 treatment group and placebo on the two co-primary efficacy endpoints will be performed using MCPMod approach. Subjects with missing primary endpoint data SES CD at Week 12/16 will be classified as "not achieved" (non-responder imputation [NRI] method) for the endoscopic remission endpoint.

The stool frequency and abdominal pain scores at an assessment visit (e.g., Week 12, Week 16) will be the average of the daily values reported during the 7 usable days preceding the scheduled assessment visit.

If 7 days daily values are not available, an average will be calculated based on the number of days with available data as follows:

- An average for the most recent 6 days will be calculated if data for only 6 days are available,
- An average for the most recent 5 days will be calculated if data for only 5 days are available,
- An average for the most recent 4 days will be calculated if data for only 4 days are available.

If the minimum number of days of diary data (i.e., 4 days for SF and AP) are not available, then the subject's score for that visit will be considered missing and NRI will be used for any endpoints (e.g., clinical remission) relating to data for this visit. Subjects who discontinue prior to Week 16 for any reason will be considered as "not-achieved" for clinical remission endpoint. Diary entries should not be included in the 7 days evaluated prior to the visit if: (1) the day the subject received medication for bowel preparation prior to endoscopy, (2) the day the subject underwent an endoscopy, and (3) 2 days following the endoscopy. Earlier diary entries will be used accordingly in order to provide the most recent data for 7 days prior to the respective study visit.

The dose-response relationships among the five ABT-494 treatment groups and placebo group will be characterized for the primary endpoints endoscopic remission at Week 12/16 and clinical remission at Week 16 using MCPMod approach. The following models will be considered: linear,  $E_{max}$ , exponential, logistic and sigEmax. The MCPMod approach for trial analysis stage consists of two main steps: MCP and Mod step. The MCP step focuses on establishing evidence for a drug effect across the doses, i.e., detecting a statistically significant dose response signal for the clinical endpoint and patient population investigated in the study. This step will typically be performed using

an efficient test for trend, adjusting for the fact that multiple candidate dose response models are being considered. If a statistically significant dose response signal has been established, one proceeds with determining a reference set of significant dose response models by discarding the non-significant models from the initial candidate set.

The response function will be the log odds (logit) of the proportion of subjects with endoscopic/clinical remission. The fitted curve will be shown graphically with confidence intervals for each dose. Estimates of the treatment differences in the response function and associated 95% confidences for each active dose against placebo will be calculated from the model. These results will be back-transformed to give point estimates of the difference in proportions and associated 95% confidence intervals.

#### **8.1.6.1.2        Sensitivity Analysis of the Primary Efficacy Variable**

The following sensitivity analyses for the primary endpoint of endoscopic remission will be conducted:

- A sensitivity analysis using observed cases, which excludes those subjects with missing post-baseline endoscopy, will also be done.

The following sensitivity analyses for the primary endpoint of clinical remission will be conducted:

- An analysis of observed cases, which excludes those subjects with missing SF or AP data at scheduled assessment visits.
- The primary analysis will be repeated using mixed-imputation. Subjects who discontinue prior to Week 16 due to lack of efficacy or adverse events will be considered as "not achieved" for the clinical remission. Subjects who discontinue for other reasons will be categorized according to LOCF.

Subgroup (characterized by the varying inclusion and exclusion criteria) analysis for the primary endpoints, clinical remission and endoscopic remission will be conducted.

**8.1.6.2 Secondary Efficacy Variables****8.1.6.2.1 Analysis of Secondary Endpoints**

Secondary efficacy variables are divided into two groups. The first group includes double-blind induction treatment period secondary endpoints. Analyses for the first group of secondary endpoints will be performed using MITT analysis set. The second group includes double-blind extension phase secondary endpoints. Analyses for the second group of secondary endpoints will be performed using ITT-N and ITT-NR analysis sets.

For categorical secondary endpoints, the pairwise comparisons for the difference in proportions of subjects between treatment groups will be analyzed using the CMH test adjusted for randomization stratification variable(s), Crohn's disease severity (SES-CD  $< 15$ ,  $\geq 15$ ) at Baseline and prior anti-TNF use (naïve, experienced). Additionally, the CMH-based 95% confidence interval for the difference in proportions will be provided. The non-responder imputation will be used for subjects with missing data at the endpoint evaluated. The last observation carried forward (LOCF) method will also be used as the sensitivity analyses for the secondary endpoints.

In general, continuous secondary efficacy variables with repeated measurements will be analyzed using a Mixed Effect Repeated Measure (MMRM) model. Continuous secondary efficacy variables will also be analyzed using an Analysis of Covariance (ANCOVA) model including factors for treatment group and stratification variable, Crohn's disease severity (SES-CD  $< 15$ ,  $\geq 15$ ) at Baseline and prior anti-TNF use (naïve, experienced). Baseline values will be used as a covariate in the MMRM and ANCOVA models. The MMRM analysis is considered primary for inferential purposes.

**8.1.6.3 Additional Efficacy Endpoints****8.1.6.3.1 Analysis of Additional Endpoints**

The pairwise comparisons for the difference between treatment groups for the additional categorical and continuous endpoints will be analyzed similarly as the secondary endpoints.

### **8.1.6.4        Multiple Comparisons**

The MCP step in MCPMod approach will typically be performed using an efficient test for trend, adjusting for the fact that multiple candidate dose response models are being considered.

### **8.1.7        Safety Analysis**

Adverse events (AEs), laboratory data and vital signs are the primary safety parameters in this study. All safety comparisons will be performed between treatment groups using the safety analysis set. Treatment-emergent AEs are defined as events that begin or worsen either on or after the first dose of the study medication and within 30 days after the last dose of the study medication. AEs will be summarized separately for: 1) double-blind induction period; 2) double-blind extension phase; 3) over the entire 52-week study duration. An overview of treatment-emergent AEs, including AEs of special interest such as adverse events leading to death and adverse events leading to early termination (see details in the SAP), AEs by Medical Dictionary for Drug Regulatory Activities (MedDRA version 15.1 or later) preferred term and system organ class, AEs by maximum relationship to study drug, and AEs by maximum severity will be summarized by number and percentage. Treatment group differences (each ABT-494 dose group versus placebo group, as well as ABT-494 dose groups combined versus placebo group) in the overall incidence of treatment-emergent AEs will be assessed with Fisher's exact test for each preferred term.

Changes in laboratory data will be described using statistical characteristics and compared between treatment groups will be performed using a one-way Analysis of Variance (ANOVA). In addition, shift tables and listings will be provided for abnormal values, whereby the normal range of the analyzing laboratory will be used. Vital signs will be analyzed similarly.

### **8.1.7.1 General Considerations**

Safety analyses will be carried out using the safety analysis set, which includes all subjects who receive at least one dose of study medication. Incidence of adverse events, including those related to study drug, changes in vital signs, physical examination results, ECGs, and clinical laboratory values will be analyzed.

Treatment-emergent adverse events will be tabulated by system organ class (SOC) and by the Medical Dictionary for Regulatory Activities (MedDRA) preferred term for each treatment group. Mean change from Baseline for laboratory and vital signs data will be summarized.

Missing safety data will not be imputed.

### **8.1.7.2 Analysis of Adverse Events**

#### **8.1.7.2.1 Treatment-Emergent Adverse Events**

Adverse events (AEs) will be coded using the Medical Dictionary for Regulatory Activities (MedDRA) dictionary. Treatment-emergent adverse events, defined as AEs that began or worsened in severity after initiation of study drug in each period of the study, will be tabulated by system organ class (SOC) and MedDRA preferred term for each treatment group.

Adverse events starting more than 30 days following discontinuation of study drug will not be included in summaries of treatment-emergent AEs. When summarizing adverse events by relationship or severity, if a subject has an event with unknown severity or relationship then the subject will be counted in the severity/relationship category of "unknown" even if the subject has a second occurrence of the same event with a severity/relationship present. The only exception is if the subject has a second occurrence of the same event with the most extreme severity (i.e., "severe") or a relationship categories of "reasonable possibility." In this case, the subject will be counted under these most extreme severity/relationship categories.

Subjects reporting more than one AE for a given MedDRA preferred term will be counted only once for that term using the most severe incident in each study period. Subjects reporting more than one type of event within an SOC will be counted only once for that SOC.

Frequencies and percentages of subjects with treatment-emergent AEs will be summarized for each treatment group as follows:

- Any event
- By system organ class, and preferred term
- By system organ class, preferred term and maximum relationship
- By system organ class, preferred term and maximum severity
- Any event and by system organ class and preferred term for events resulting in death
- Any event and by system organ class and preferred term for events resulting in study drug discontinuation
- Any event and by system organ class and preferred term for serious events
- Any event and by system organ class and preferred term for adverse events with a relationship of "reasonable possibility"
- Any event and by system organ class and preferred term for adverse events of special interest (infection, opportunistic infection, and gastrointestinal perforations, malignancies and drug related hepatic disorders)

All AEs leading to early termination of study drug will be presented in listing format.

Frequencies and percentages for any AE and for each preferred term will be compared between each of the ABT-494 dosing groups and the placebo group using a Fisher's exact test.

The adverse events of special interest (infection, opportunistic infection, and gastrointestinal perforations, malignancies and drug related hepatic disorders) will be specified in the SAP.

A listing by treatment group of treatment-emergent AEs grouped by SOC and MedDRA preferred term with subject ID numbers will be generated.

The post-treatment AEs will be summarized in the same way as the treatment-emergent AEs described above.

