11.2 Analysis of Adverse Events**11.2.1 Treatment-Emergent Adverse Events**

Treatment-emergent AE for double-blind Extension Phase is defined as any adverse event with an onset date on or after the first dose of double-blind maintenance dose and prior to the open-label dose or up to 30 days after the last dose of double-blind maintenance dose if subject discontinued prematurely in double-blind maintenance phase.

For subjects who entered open-label due to inadequate response, treatment-emergent AEs for open-label Extension Phase will also be summarized by open-label dose. Treatment-emergent AE for open-label Extension Phase is defined as any adverse event with an onset date on or after the first dose of open-label dose and up to 30 days after the last dose of open-label dose.

An overview of treatment-emergent AEs, including AEs of special interest such as adverse events leading to death and adverse events leading to early termination, AEs by

Medical Dictionary for Drug Regulatory Activities (MedDRA version 20.0 or later) preferred term and system organ class, AEs by maximum relationship to study drug, and AEs by maximum severity will be summarized by number and percentage.

Changes in laboratory data will be summarized.

In addition, shift tables and listings will be provided for abnormal values, whereby the normal range of the analyzing laboratory will be used. Vital signs will be analyzed similarly.

The number and percent of subjects experiencing treatment-emergent adverse events will be summarized for the following adverse event categories.

- Any treatment-emergent adverse event.
- Any treatment-emergent adverse event that was rated as possibly related to study drug by the investigator (Reasonable Possibility).
- Any treatment-emergent severe adverse event.
- Any treatment-emergent serious adverse event.
- Any treatment-emergent adverse event leading to discontinuation of study drug.
- Any treatment-emergent adverse event leading to death.
- Any treatment-emergent adverse event of special interest.

Treatment-emergent adverse events will be summarized as follows:

- Grouped by System Organ Class and Preferred Term.
- Grouped by System Organ Class, Preferred Term and Severity.
- Grouped by System Organ Class, Preferred Term and Relationship to Study Drug.
- Grouped by System Organ Class and Preferred Term with subject numbers.

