11.2.2 Adverse Events of Special Interest

The Adverse Events of Special Interests (AESI) categories will be summarized and presented for each treatment group using SMQ/CMQ/LMQ/Preferred Term.

| AESI | Type of MedDRA Query | Broad or Narrow Search | SMQ/CMQ/LMQ Search Criteria |
|--|----------------------|------------------------|---|
| Serious Infections | CMQ | | "Infection" – Subset for SAEs |
| Opportunistic Infection | CMQ | | "Opportunistic infection" |
| Herpes zoster | CMQ | | "Herpes zoster" |
| Tuberculosis | CMQ | | "Tuberculosis" |
| Malignancy | SMQ | Narrow | "Malignancies," |
| Non-Melanoma Skin Cancer (NMSC) | SMQ | Broad | Skin Malignant tumours (Broad SMQ) removing Melanoma CMQ |
| Malignancy other than NMSC | SMQ | Narrow | Malignancy and removing NMSC output |
| Lymphoma | SMQ | | "Malignant Lymphomas" |
| Hepatic Disorder | SMQ | Narrow | "Drug Related Hepatic disorders" |
| Intestinal Perforations | LMQ | | Terms for/related to any part of GI Tract, GI Ulcers, obstruction, hemorrhage |
| Anemia | CMQ | | "Non-Hemolytic and Non-Aplastic anemias" |
| Adjudicated Cardiovascular Events | Output from CAC | | |
| Neutropenia | CMQ | | "Hematological toxicity – Neutropenia" |
| Lymphopenia | CMQ | | "Hematological Toxicity – Lymphopenia (Veliparib Product Specific)" |
| Renal dysfunction | SMQ | Narrow | "Acute renal failure" |
| Rhabdomyolysis/myopathy | SMQ | Narrow | "Rhabdomyolysis/Myopathy" |
| Creatine phosphokinase (CPK) Elevation | Preferred Term | | "blood creatine phosphokinase increased" |

Additional AEs may be considered for tabulation/summary based on recommendations from Clinical and Safety as deemed appropriate.

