11.2.2 Adverse Events of Special Interest

The Adverse Events of Special Interests (AESI) categories will be summarized and presented for each treatment group using SMQ/CMQ.

| AESI | Type of MedDRA Query | Broad or Narrow Search | SMQ/CMQ Search Criteria |
|--|----------------------|------------------------|---|
| Infection | CMQ | | "Infection" |
| Serious Infection | CMQ | | "Infection" – Subset for SAEs |
| Opportunistic Infection | CMQ | | "Opportunistic infection" |
| Herpes zoster | CMQ | | "Herpes zoster" |
| Tuberculosis | CMQ | | "Tuberculosis" |
| Malignancy | SMQ | Narrow | "Malignancies," "Malignant lymphomas" |
| Non-Melanoma Skin Cancer (NMSC) | SMQ | Narrow | "Skin neoplasms, malignant and unspecified" |
| Malignancy other than NMSC | | | |
| Hepatic Disorder | SMQ | Narrow | "Drug Related Hepatic disorders" |
| Gastrointestinal Perforations | SMQ | Narrow | "Gastrointestinal perforation" |
| Anemia | CMQ | | "Non-Hemolytic and Non-Aplastic anemias" |
| Adjudicated Cardiovascular Events | Output from CAC | | |
| Neutropenia | CMQ | | "Hematological toxicity – Neutropenia" |
| Increased serum creatinine and renal dysfunction | SMQ | Narrow | "Acute renal failure" |
| Elevated creatine phosphokinase | SMQ | Narrow | "Rhabdomyolysis/myopathy" |

Additional AEs may be considered for tabulation/summary based on recommendations from Clinical and Safety as deemed appropriate.

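### The Extension SAP drops the protocol's all-infection AESI and limits the general infection query to SAEs, without declaring the change

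*Protocol*

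**What the plan says.** Protocol 8.1.7.2.1 lists the frequency tables to be produced for each treatment group. One is by system organ class and "preferred term for adverse events of special interest (infection, opportunistic infection, and gastrointestinal perforations", with malignancies and drug-related hepatic disorders completing the list. The same section returns to the list later: "The adverse events of special interest (infection, opportunistic infection, and gastrointestinal perforations, malignancies and drug related hepatic disorders) will be specified in the SAP". Infection stands there with no seriousness qualifier and apart from opportunistic infection. Protocol 8.1.7 sets the periods: "AEs will be summarized separately for: 1) double-blind induction period; 2) double-blind extension phase; 3) over the entire 52-week study duration".

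The two SAPs implement this differently.

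- **Induction SAP, 11.2.2:** one row applies the whole Infection CMQ, and a separate row, "Serious Infection", applies its SAE subset.
- **Extension SAP, 11.2.2:** the only row using the general Infection CMQ is "Serious Infections", again the SAE subset. Opportunistic infection, herpes zoster and tuberculosis have their own rows with no seriousness limit.

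Both SAPs put the line "Any treatment-emergent adverse event of special interest" in the adverse event overview (11.2.1). The Extension SAP also asks for rates per 100 patient-years for the overview, with the number of events as numerator. It produces the overview for the Any ABT-494 set as well. Its section 12.1, on differences from the protocol, lists efficacy variables only.

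**The concern.** The protocol promises a summary of infections of any seriousness as a special-interest category, for the extension as well as for induction. The Extension SAP does not deliver it and does not say so. The extension is the longer of the two phases (36 weeks against 16), and every subject in it is on active drug. Protocol 6.1.7 asks sites to watch closely for infection and to test promptly when a new one appears, so infection of any grade is something the trial set out to follow.

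At stake are one pre-specified safety category and one headline figure. The any-AESI row carries the same label in both SAPs but has different infection content, and the label does not tell a reader that the definition has moved.

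**Working it through.** The plan states no figure to reproduce, so the check is a side-by-side reading of the lists.

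| Category | Protocol 8.1.7.2.1 | Induction SAP 11.2.2 | Extension SAP 11.2.2 |
|---|---|---|---|
| Infection, any seriousness | named | whole Infection CMQ | no row |
| Serious infection | not named separately | Infection CMQ, SAEs only | Infection CMQ, SAEs only |
| Opportunistic infection | named | CMQ | CMQ |
| Herpes zoster | not named | CMQ | CMQ |
| Tuberculosis | not named | CMQ | CMQ |
| Perforation | named | narrow SMQ | LMQ that also takes in ulcers, obstruction and hemorrhage |
| Malignancy | named | narrow SMQ, lymphoma included | narrow SMQ, lymphoma in its own row |
| Non-melanoma skin cancer | not named | narrow SMQ | broad SMQ less melanoma |
| Drug-related hepatic disorder | named | narrow SMQ | narrow SMQ |
| Lymphopenia | not named | no row | CMQ |
| CPK elevation | not named | through the rhabdomyolysis/myopathy SMQ | that SMQ plus a separate preferred term |

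1. Infection-related categories number 2 in the protocol, 5 in the Induction SAP and 4 in the Extension SAP (5 − 1 = 4). The missing one is the all-infection row.
2. Of the five categories the protocol names, four still have a row in the Extension SAP. Infection is the only one without.
3. The Induction SAP was written against Amendment 4 and the Extension SAP against Amendment 5. The itemised changes in protocol Appendix J contain none to 8.1.7.2.1, so the amendment does not explain the removal.
4. What leaves the AESI table can be written down. Let s be the share of infections that are serious, and o the share that are non-serious but caught by the opportunistic, zoster or tuberculosis rows. Ignoring any overlap with non-infection rows, the omitted share is 1 − s − o. The documents give neither s nor o. As an illustration only, an assumed s + o of 5% to 40% gives an omitted share of 1 − 0.05 = 95% down to 1 − 0.40 = 60%. The omitted share exceeds one half only if s + o is below 50%.
5. The overview row and the rate are affected differently. The row counts subjects, so it loses only those whose sole AESIs were infections of the omitted kind. The rate counts events, so it loses every such event.

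Step 5 takes the any-AESI row to be the union of the 11.2.2 categories. The Extension SAP gives no other list; 11.2.1 only mentions deaths and early terminations loosely as examples.

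**The case against.** The strongest reply is that nothing is lost. All extension events are tabulated by system organ class and preferred term, by severity and by relationship, with rates per 100 patient-years, so non-serious infections remain visible by dose. The summaries are descriptive, and all extension dose groups share one definition, so comparisons between doses within the extension are internally consistent. The protocol leaves AESI specification to the SAP, and the Extension SAP allows further tabulations on clinical advice.

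Most of this stands and limits the weight of the point. Two parts do not answer it. Leaving the specification to the SAP, for categories the protocol has already named, is most naturally read as leaving the search terms to it, not as permission to remove a category. An optional later tabulation is also not a pre-specified one. The general tables do not feed the AESI table or the any-AESI row, and since the content of the Infection CMQ is not given, it cannot be shown to equal any system organ class total.

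Several stronger readings are tempting, and the documents do not support them:

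- **That only serious infections are kept.** Opportunistic infection, zoster and tuberculosis of any seriousness remain.
- **That most infections are omitted.** This is plausible, but it depends on s + o, which the documents do not give.
- **That protocol 3.2 names all infection as a class concern.** It names serious infection and herpes zoster, in discussing a non-selective JAK inhibitor. The argument rests on 8.1.7.2.1.
- **That the definition shifts part-way through the cumulative summary.** The Any ABT-494 analysis is specified in the Extension SAP, which has a single AESI table. The narrower point is that a non-serious infection during induction can be an AESI in the induction report and not in the cumulative one.
- **That any-AESI will fall from induction to extension because of the definition.** Neither SAP plans that comparison, the phases differ in length and population, and the wider perforation and skin cancer searches and the added rows could push the figure the other way.

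**Conclusion.** The point holds in a limited form. A safety category that the protocol requires is missing from the Extension SAP, and the change is undeclared. As a result, non-serious infections other than opportunistic infection, zoster and tuberculosis drop out of the extension AESI table, the any-AESI row and its rate. They remain in the tables by system organ class and preferred term. No hypothesis test or efficacy result is touched.

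The size cannot be derived from the documents. The 60% to 95% range rests wholly on the assumed s + o and should not be cited as a finding. The conclusion does not depend on it, because the mismatch is in the text. The net direction of any difference in any-AESI between phases is also unknown, since other AESI searches changed at the same time.

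**What to change.** Add a row to the Extension SAP 11.2.2 table with category Infection, query type CMQ and search term Infection, as in Induction SAP 11.2.2. Carry it into the any-AESI overview row and the rates per 100 patient-years, by double-blind dose, by open-label dose and in the Any ABT-494 set.

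That row alone will not make any-AESI comparable with induction. Section 12.1 should therefore list every AESI change: perforation from SMQ to LMQ, non-melanoma skin cancer from narrow to broad, and the added lymphopenia row and CPK preferred term. The any-AESI row should be labelled as not directly comparable with induction. If leaving infection out is deliberate, 12.1 should say so and give the reason.

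The cost is one table row, using a query already specified for induction, and a short addition to 12.1. The downside for the sponsor is that any-AESI in the extension becomes less favourable: adding a category can only raise the figure or leave it unchanged.
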